5.2. DEATH

The following summaries on death events will be provided:

- An overview of all death events that occurred during the blinded/open-label treatment period, and primary cause of death
- TEAEs leading to death (death as an outcome on the AE report page as reported by the Investigator), by primary SOC and PT
- TRAEs leading to death, by primary SOC and PT
- Listing of all TEAEs leading to death
- Listing of all death events

5.3. LABORATORY SAFETY VARIABLES

5.3.1. Definitions

Clinical laboratory data consists of blood analysis, including hematology and serum chemistry. Clinical laboratory values in conventional units will be converted using the international system of units (SI).

The laboratory parameters will be classified as follows:

- **Hematology** (blood sample: ethylenediaminetetraacetic acid) will include hemoglobin, , white blood cell (WBC) count, lymphocytes, neutrophils, platelets. WBC differential

may be automated or manual as per institutional standards. Reticulocytes may be done only when clinically indicated.

- **Serum Chemistry** (blood sample: serum)

- Complete Serum Chemistry will include sodium, potassium, chloride, bicarbonate, blood urea nitrogen (BUN), creatinine, glucose, calcium, phosphate, magnesium, ALT, AST, alkaline phosphatase, total bilirubin, lactate dehydrogenase (LDH), total protein, albumin, creatinine kinase, uric acid.
- Limited Serum Chemistry will include sodium, potassium, chloride, bicarbonate, BUN, creatinine, glucose, ALT, AST, alkaline phosphatase, total bilirubin, and LDH.
- If the total bilirubin concentration is increased above 1.5 times the upper normal limit, total bilirubin should be differentiated into the direct and indirect reacting bilirubin.

5.3.2. Analysis of Laboratory Variables

Whenever applicable, severity of selected clinical laboratory measures will be determined based on the CTCAE criteria. Laboratory values with CTCAE Grade ≥ 3 will be presented in a data listing. The worst toxicity grade in hematology and chemistry will be summarized by toxicity grade. Shift tables that present changes from baseline to worst on-study relative to CTCAE classification ranges will be presented. These shift tables will include results from unscheduled visits.

For selected key laboratory parameters, box plots on measurements over time as well as by-patient plots for patient-level measurements over time may be presented.

A listing of cases where ALT or AST > 3 x upper limit of normal (ULN) with simultaneous total bilirubin > 2 x ULN will be presented.

Thresholds/Range analyses for selected laboratory parameters will be conducted. The number and percentage of patients classified into each category based on worst values will be presented.

5.4. VITAL SIGNS, ECOG, AND PHYSICAL EXAMINATION VARIABLES

The physical examination (PE) will be performed according to the standards at each institution.

Physical examination, including vital signs, will be performed on the scheduled day, even if study treatment is being interrupted. Physical examinations should include general appearance, dermatological, head, eyes, ears, nose, throat, respiratory, cardiovascular, abdominal, lymph nodes, musculoskeletal, and neurological examinations.

Vital signs include height (without shoes) in centimeters (cm), weight (indoor clothing without shoes) in kilograms (kg), body surface area (BSA), systolic and diastolic blood pressure (SBP and DBP), pulse measurements, and body temperature ($^{\circ}$ C). BSA will be calculated by the Dubois ([Dubois 1916](#)) method.

An ECOG score assessment with grades 0-5 will be performed during screening, day 1 of each cycle, and EoBT and/or EoT visits.

The actual value and change from baseline to each on-study evaluation will be summarized for vital signs including pulse, temperature, systolic blood pressure, diastolic blood pressure, BSA and weight. Shift tables that present changes from baseline to highest on-study and lowest on-study for systolic blood pressure and diastolic blood pressure will be presented. Shift tables that present changes from baseline to worst on-study and last on-study ECOG performance status values will also be produced.

Abnormal vital signs results will be summarized in the threshold/range analyses.

Abnormal PE findings will be provided in a data listing.

5.5. ELECTROCARADIOGRAM (ECG)

Standard 12-lead ECGs will be performed. The ECGs performed on Day 1 of Cycles 1 and 2 during blinded study treatment are to be performed just prior to the blood sample taken 2 hours postdose (approximately at the expected t_{max} of plasma selinexor). ECGs may also be performed as clinically indicated during the study.

Patients must rest for at least 5 minutes prior to the ECG recording. The Investigator will interpret the ECG using one of the following categories: normal, abnormal but not clinically significant, or abnormal and clinically significant. The following will be assessed: heart rate, PR interval, QT interval, QRS interval, and QT corrected Bazett's or Fredericia's formula.

Changes from baseline to highest on-study post baseline measurement for PR interval, QRS interval, and QT corrected will be summarized using shift tables. For heart rate, changes from baseline to lowest and highest on-study post baseline measurement will be presented.

Abnormal ECG results will be summarized in the threshold/range analyses.

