10.6.1.4. Electrocardiography

Standard 12-lead ECGs will be performed. The ECGs performed on Day 1 of Cycles 1 and 2 during blinded study treatment are to be performed just prior to the blood sample taken 2 hours postdose (approximately at the expected t_{\max} of plasma selinexor). ECGs may also be performed as clinically indicated during the study.

Patients must rest for at least 5 minutes prior to any ECG recording. The Investigator will interpret the ECG using one of the following categories: normal, abnormal but not clinically significant, or abnormal and clinically significant. The time the ECG was performed and the following parameters will be recorded in the eCRF: heart rate, PR interval, QT interval, QRS interval, and QT corrected using either Bazett's or Fredericia's formula.

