2.6. BASELINE MEASUREMENT

For blinded treatment period, the baseline value is defined as the latest value prior to the first dose of blinded study treatment. In the case an assessment performed on the same date as the first dosing date, but it is impossible to determine the evaluation time relative to the time of taking the first dose, the evaluation time will be assumed to be following the protocol-defined schedule.

For patients who proceed to open-label period, the baseline value for assessments in open-label treatment period will be the latest value prior to the date of first open-label study treatment.

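### SAP 5.5 names no QT correction formula, so Bazett and Fridericia values can enter the same QTc shift table

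*SAP*

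**What the plan says.** Protocol 10.6.1.4 lists the ECG parameters to be entered in the eCRF. They include heart rate, the uncorrected QT interval, "and QT corrected using either Bazett's or Fredericia's formula". Nothing there says which formula a site should use, or that it should stay the same within a site or a patient. ECGs are read locally: "The Investigator will interpret the ECG using one of the following categories: normal, abnormal but not clinically significant, or abnormal and clinically significant". No central ECG reading is described.

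SAP 5.5 lists the parameters to be assessed with the same open choice: "heart rate, PR interval, QT interval, QRS interval, and QT corrected Bazett's or Fredericia's formula". It then treats corrected QT as one parameter: "Changes from baseline to highest on-study post baseline measurement for PR interval, QRS interval, and QT corrected will be summarized using shift tables". A second summary follows: "Abnormal ECG results will be summarized in the threshold/range analyses". Neither summary is tied to a formula.

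Baseline comes from SAP 2.6: "the baseline value is defined as the latest value prior to the first dose of blinded study treatment". No same-formula condition is attached. By Protocol Table 1 and its ECG footnote, the Cycle 1 Day 1 and Cycle 2 Day 1 ECGs are taken about 2 hours after dosing. The scheduled baseline is therefore the screening ECG. The scheduled on-study ECGs are those two and the end-of-blinded-treatment ECG, with unscheduled ECGs where clinically indicated.

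**The concern.** A shift table compares two readings from the same patient, so both should be on the same scale. Bazett and Fridericia give the same value only at 60 beats/min. Above that rate Bazett is higher, and the gap widens as the rate rises. If the baseline value used one formula and the highest on-study value used the other, the patient can change category with no change in repolarisation. Because the on-study value is the highest of several, a Bazett reading at a fast heart rate is more likely to be the one selected. The threshold analyses have the same weakness, since one cut-off would mean different things under the two formulas.

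At stake is how readable the only QTc summaries in the plan are. The formula is also left to be settled at programming, although it could be fixed in one sentence beforehand.

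**Working it through.** Neither document gives a QTc figure, so there is nothing to reproduce. The check has two parts: whether any text settles the formula, and how far apart the formulas are.

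**Does any text settle the formula?**

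- SAP 5.5 and Protocol 10.6.1.4 both leave the choice open.
- SAP 2.6 sets baseline by timing only.
- The sponsor's programming rule book is cited in SAP 2.2.2 and 2.2.3 for date and age imputation only.
- The SAP reference list includes the source paper for the Fridericia correction and none for Bazett. No SAP text cites that paper.
- SAP 5.4 handles a parallel case. Protocol 10.6.1.2 allows two formulas for body surface area, and SAP 5.4 fixes one. SAP 5.5 has no equivalent sentence.

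**How far apart are the formulas?**

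Standard definitions, with RR = 60/HR in seconds:

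- QTcB = QT / RR^(1/2)
- QTcF = QT / RR^(1/3)
- Hence QTcB = QTcF × RR^(-1/6) = QTcF × (HR/60)^(1/6)

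Heart rate and QT values are assumptions, because the documents give none.

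Same ECG, assumed QTcF = 420 ms:

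- 60 beats/min: 420 × 1.000 = 420 ms, difference 0
- 70 beats/min: 420 × 1.026 = 430.9 ms, difference +10.9
- 80 beats/min: 420 × 1.049 = 440.6 ms, difference +20.6
- 90 beats/min: 420 × 1.070 = 449.4 ms, difference +29.4
- 100 beats/min: 420 × 1.089 = 457.3 ms, difference +37.3

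The same comparison over an assumed uncorrected QT of 340 to 400 ms gives, for QTcB minus QTcF: -10 to -11 ms at 50 beats/min, +9 to +11 at 70, +18 to +22 at 80, +27 to +32 at 90 and +36 to +42 at 100. The result does not hang on the choice of 420 ms.

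Within one patient, QTcF held at 420 ms and heart rate rising from 70 to 90 beats/min:

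- Fridericia at both visits: 420 to 420, shift 0.
- Bazett at both visits: 430.9 to 449.4, shift +18.4 (unrounded values). This is Bazett's own dependence on heart rate, not an effect of mixing.
- Fridericia at baseline, Bazett on study: 420 to 449.4, shift +29.4.
- Bazett at baseline, Fridericia on study: 430.9 to 420, shift -10.9. A switch can therefore hide an increase as well as create one.

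For an assumed QTcF of 400 to 430 ms, Fridericia followed by Bazett gives +28 to +30 ms in this scenario. If heart rate stays at 70 and only the formula changes from Fridericia to Bazett, the shift is +10.9 ms at a QTcF of 420 ms.

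If one formula is derived for every ECG, the artefact from switching is 0 by construction. With Fridericia, the shift in these constant-QTcF scenarios is also 0. With Bazett throughout, about 10 to 27 ms remains for the heart-rate rises tried (60 to 70 up to 70 to 100 beats/min, QTcF 400 to 430 ms).

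**The case against.** The SAP does not say that it combines the formulas. A reader might infer from the single table that pooling is planned, but the text supports only that the formula is unspecified. The eCRF layout and table shells are not in the documents, and the unreferenced Fridericia paper is some sign that Fridericia was meant. This stands. Pooling is what the text permits if followed literally, not a stated intention.

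A reader might also infer that a QTc shift could not be attributed to the drug. The documents do not support that. The trial is randomised and placebo-controlled, and SAP 5 reports safety by arm received. If formula choice follows site practice, the mix should be roughly balanced between arms, and the comparison with placebo stays informative. What suffers is the precision of that comparison and the meaning of an individual shift.

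It is tempting to argue that selinexor raises heart rate, so that Bazett would bias the arms differently. No heart-rate data are given, and that argument would apply to Bazett used throughout, so it says nothing about mixing. SAP 5.5 also tabulates heart-rate change, so an imbalance would be visible. Nor do the documents say that the ECGs near expected tmax were timed to detect a QT effect; they give only the timing. The safety endpoints in Protocol 7.5.4 do not list ECG, and SAP Table 5-1 has no QT or cardiac category of clinical interest.

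Finally, the larger figures need a formula switch and a fast heart rate together. The plan allows a switch but does not show that any occurred. SAP 5.5 gives no shift categories or cut-offs, so the number of patients who would change category cannot be computed.

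**Conclusion.** The point holds as a minor one. Two formulas are allowed at recording, one undifferentiated parameter is summarised, and no rule separates or harmonises them. For an assumed QTcF of 420 ms, the formulas differ on the same ECG by about +11 to +37 ms at 70 to 100 beats/min. That is enough to add noise and to create or hide an apparent shift within a patient. These sizes rest on assumed QT and heart-rate values, and how often formulas would be mixed is unknown.

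The effect is confined to descriptive safety output, which SAP 5 says will not be systematically tested. PFS, OS, type I error and sample size are untouched. It remains more than missing detail, because the data for a better method are already collected and SAP 5.4 takes the equivalent step for body surface area.

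**What to change.** In SAP 5.5:

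- Name one formula for all QTc summaries, for example QTcF = QT / RR^(1/3) with RR = 60/HR.
- Derive it from the recorded QT and heart rate for every ECG, including baseline.
- Use only that derived value in the shift table and the threshold/range analyses.
- If a second formula is wanted, derive it for all ECGs in the same way and show it in a separate table.
- Keep site-reported QTc in listings.

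Naming any single formula removes the mixing. Fridericia also avoids the Bazett heart-rate artefact in the scenarios above. The cost is a few lines of SAP text and one derived variable, with no new data, visits or protocol amendment.

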9.1.6. End of Blinded Treatment Visit; Return to the Clinic

At the time a patient permanently discontinues blinded study treatment or has PD prior to unblinding of all patients at the end of Phase 3 (ie, when the required number of PFS events for the primary PFS analysis are observed), a visit should be scheduled as soon as possible (within 14 days), at which time all of the assessments listed for the End of Blinded Treatment (EoBT) Visit will be performed. Study procedures will be performed ≤ 14 days after the last dose of study treatment, as specified in Table 1. An EoBT CRF page will be completed, giving the date and reason for stopping the study treatment. Patients lost to follow-up should be recorded as such on the appropriate eCRF.

For patients proceeding to open-label selinexor, the EoBT Visit will serve as the baseline for the open-label treatment phase. After the unblinding following the PFS analyses, patients in the selinexor arm who are continuing on selinexor but as open-label treatment must complete their EoBT Visit before their next scheduled selinexor dose.

- Informed consent for open-label selinexor (only for patients proceeding to open-label selinexor) and Assent Form for adolescent patients (permitted only in countries in

which adolescents have been approved by the national/local regulatory/ethical authority)

- Physical examination and vital signs (blood pressure, pulse, and body temperature) (Section 10.6.1.1)
- Weight, height, and BSA (Section 10.6.1.2)
- ECOG performance status assessment (Section 10.6.1.3)
- 12-lead ECG (Section 10.6.1.4)
- Urinalysis (Section 10.6.2.1)
- Hematology (Section 10.6.2.1)
- Complete serum chemistry (Section 10.6.2.1)
- Coagulation tests (Section 10.6.2.1)
- Serum hCG pregnancy test (females of childbearing potential only). Females of childbearing potential who are proceeding to open-label selinexor must have a negative serum hCG pregnancy test at the EoBT Visit (or within 3 days before the first dose of open-label selinexor). (Section 10.6.2.2)

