9.2. Description of Study Days: Open-label Selinexor

Please note:

- EoBT Visit serves as baseline of Open-Label Selinexor; The EoBT Visit may occur on the day of the patient's first open-label dose (OL-C1 D1 Visit) but must be ≤ 14 days of last blinded dose. OL C1 D1 must occur within 14 days of the EoBT Visit.
- Patients in the selinexor arm who continue selinexor but as open-label treatment must complete the EoBT Visit before their next scheduled selinexor dose to maintain continuity of selinexor dosing from blinded to open-label treatment.
- Physical examination assessments and laboratory assessments done at the EoBT Visit do not need to be repeated at OL C1 D1.

9.2.1. Visits OL1-6 (Cycle 1: Days 1, 8*, 15*, 22, 29*, and 36* [± 1 days]); Return to the Clinic

There are six clinic visits (ie, Days 1, 8*, 15*, 22, 29*, and 36*) during the first six-week cycle (Cycle 1).

Visits (ie, Days 8, 15*, 29*, and 36*) are not required for patients who continue selinexor but as open-label treatment.

The following study assessments will be performed during Cycle 1, as specified in [Table 2](#).

- Physical examination and vital signs (blood pressure, pulse, and body temperature) (Days 8*, 15*, 22, 29*, and 36*) [Section 10.6.1.1](#)
- Weight (Days 8*, 15*, 22, 29*, and 36*) ([Section 10.6.1.2](#))
- Limited serum chemistry (Days 8*, 15*, 22, 29* and 36*) ([Section 10.6.2.1](#))
- Tumor biopsy, only for patients who cross over from blinded placebo to open-label selinexor and have sufficient material available from a biopsy sample obtained during blinded study treatment (pre- or post-dosing) within 12 months prior to the first dose of open-label selinexor (Day 22 only). Note: If the biopsy is not performed on Cycle 1 Day 22, it may be performed on Cycle 2 Day 1 (see [Section 9.2.2](#)). Patients in the selinexor arm who continue on selinexor but as open-label treatment are not required to have an additional tumor biopsy on Cycle 1 Day 22 of open-label treatment. See [Section 10.11.3](#) for biopsy details.
- CCI
- CCI
- Nutritional consultation (should occur on Day 1 before the first dose of open-label selinexor) for patients in the placebo arm who cross over to open-label selinexor. The nutritional consultation is not required at C1 D1 of open-label selinexor treatment for patients in the selinexor arm who continue on selinexor but as open-label treatment. See [Section 10.7.3](#).
- Selinexor: in clinic dosing and dispensing of for home use

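### SAP 5.5 lists no by-arm estimate of ECG change at the two peak-timed ECGs, and the planned highest-value shift table is a less sensitive substitute

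*SAP*

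**What the plan says.** **ECG schedule.** Under SAP 5.5 and protocol 10.6.1.4, the ECGs on Day 1 of Cycles 1 and 2 "are to be performed just prior to the blood sample taken 2 hours postdose", which both documents place near the expected tmax. Protocol Table 1 has no scheduled ECG from Cycle 3 onward. One more is taken at the EoBT visit (protocol 9.1.6), with no timing relative to a dose beyond the visit window: "Study procedures will be performed ≤ 14 days after the last dose of study treatment". SAP 5.5 also allows unscheduled recordings: "ECGs may also be performed as clinically indicated during the study".

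**ECG analysis.** SAP 5.5 plans two things for PR, QRS and QTc. One is "Changes from baseline to highest on-study post baseline measurement for PR interval, QRS interval, and QT corrected will be summarized using shift tables". The other is "Abnormal ECG results will be summarized in the threshold/range analyses", with no cut-offs given. Heart rate gets its lowest and highest changes.

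**Window and baseline.** SAP 5 presents blinded-period safety data. SAP 2.4 runs that period to 30 days after the last dose, or to an earlier new antineoplastic treatment, so it normally includes the EoBT ECG. For selinexor patients who continue open-label, the period runs on through open-label dosing. For placebo patients who cross over, it stops before the first open-label dose. Baseline is the last value before the first dose (SAP 2.6), normally the screening ECG.

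**Comparison.** SAP 5.4 plans actual values and change from baseline at each evaluation for vital signs. SAP 5.5 has no such line for ECG.

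**The concern.** Timing an ECG to the expected peak is useful only if that recording is analysed as a timed measurement. The highest post-baseline value mixes the two peak ECGs with one that may fall up to 14 days after the last dose, and it depends on how many ECGs a patient has. The shift table then turns a continuous measurement into categories. Neither step yields an arm mean, a difference from placebo or an interval.

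At stake is how precisely the report can describe a QTc effect. With 285 patients randomized 2:1 against placebo, the timed ECGs could estimate a mean difference to within a few milliseconds. A small effect, around 5 ms, could pass unnoticed in the planned tables. No primary or key secondary efficacy result depends on this.

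**Working it through.** The documents give no QTc effect, SD or power figure, so there is nothing of the plan's own to reproduce.

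**Inputs from the documents.** 285 patients randomized 2:1 (SAP 1.1), hence 285 × 2/3 = 190 and 285 × 1/3 = 95. One baseline, two peak ECGs and one EoBT ECG.

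**Assumed inputs.** Mean QTc 420 ms; between-patient SD 18 ms; within-patient SD *w* from 8 to 20 ms; peak effect *d* of 5, 10 or 20 ms on the two timed ECGs and none at EoBT (the least favourable case for the plan); every patient has all four ECGs. Two-sided 5% tests serve only as a yardstick.

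**Step 1: what taking the highest value costs.** As *d* approaches 0, the share of the effect kept in the selinexor-minus-placebo difference equals the chance that the highest of the three ECGs is a peak one: 2/3. Larger effects keep more. By simulation over *w* = 8, 12 and 20 ms:

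| Peak effect | Share kept | Share lost |
|---|---|---|
| 5 ms | 71–74% | 26–29% |
| 10 ms | 73–81% | 19–27% |
| 20 ms | 79–89% | 11–21% |

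Noise alone raises the placebo highest value above baseline by about 7, 10 and 17 ms, but this happens in both arms and cancels when the ECG counts are equal.

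**Step 2: what the timed ECGs could give.** For the mean of the two peak ECGs adjusted for baseline:

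residual variance = 18² + *w*²/2 − (18²)² / (18² + *w*²)

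SE = √(residual variance) × √(1/190 + 1/95) = √(residual variance) × 0.1257

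| *w* (ms) | Residual variance | SE (ms) | 5/SE − 1.96 | Detection of 5 ms |
|---|---|---|---|---|
| 10 | 324 + 50 − 247.6 = 126.4 | 1.41 | 1.58 | 94% |
| 15 | 324 + 112.5 − 191.2 = 245.3 | 1.97 | 0.58 | 72% |
| 20 | 324 + 200 − 145.0 = 379.0 | 2.45 | 0.08 | 53% |

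Simulation gives 94%, 71% and 51%, in agreement.

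**Step 3: what the categories give.** Take *w* = 12 ms, *d* = 5 ms and categories cut at 450, 480 and 500 ms (assumed). An upward shift of the highest value occurs in 10.8% of placebo and 15.3% of selinexor patients, a difference of 0.0449 before rounding.

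- Pooled SE = √(0.1376 × 0.8624 × (1/190 + 1/95)) = 0.0433.
- Unpooled SE = 0.0411.
- (0.0449 − 1.96 × 0.0433)/0.0411 = −0.97, so detection is 17%.

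At the same SD, the unadjusted mean change at the two peak ECGs detects 5 ms in 77% of trials. For *w* of 10 to 20 ms, counts of rises above 30 ms or of new values above 450 ms detect 5 ms in about 11 to 17%.

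**Step 4: which step costs more.** At *w* = 12 ms, restricting the same categories to the peak ECGs raises detection only from 15–17% to 23–25% at 5 ms, and from 57–71% to 74–84% at 10 ms. Categorising is the larger loss. At 20 ms, detection exceeds 99% either way.

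**Step 5: unequal ECG counts.** Protocol Table 2 schedules ECGs at open-label Cycle 1 Day 1 (not repeated if done at EoBT) and at the end-of-treatment visit. These can enter the highest value for selinexor rollover patients but not for placebo crossovers. As an upper bound, two extra ECGs in every selinexor patient, with no drug effect, give a spurious difference of 2.5 to 6.3 ms. The SAP calls these patients few, so the actual bias should be far smaller.

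**The case against.** **The general rule may already cover this.** SAP 2.1 displays summary statistics at each scheduled time point where applicable, with mean and SD for continuous variables. This stands in part: by-visit ECG means might be produced under it. But 5.5 does not list them, 5.4 does so for vital signs, and neither 2.1 nor 5.5 provides a between-arm difference or interval.

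**Another plan may use the timed ECGs.** They are tied to a blood sample, and SAP 2 sends a redacted set of analyses to a separate plan. This stands as a limit: the point concerns what SAP 5.5 lists, not what may exist elsewhere.

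**No testing or QTc claim is planned.** SAP 5 is essentially descriptive, and protocol 7.5.4 does not name ECG among the safety evaluations. This is correct, so the detection rates are only a yardstick. An estimated difference with an interval is still descriptive.

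**The precision is optimistic.** Every SD and cut-off is assumed, attrition before Cycle 2 is ignored, and protocol 10.6.1.4 allows either of two QT correction formulas. This stands, and is why the fix asks for one stated formula.

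**Pooling is inferred.** SAP 5.3.2 explicitly includes unscheduled visits in the laboratory shift tables; 5.5 is silent for ECG. Including EoBT and unscheduled ECGs is the natural reading but is not stated.

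**Conclusion.** The point holds as a cheap improvement to the safety analysis. SAP 5.5 lists no summary of QTc, PR or QRS change at the two peak-timed ECGs and no between-arm estimate. Under the assumptions above, the highest-value approach dilutes a 5 to 10 ms peak effect by roughly 20 to 30%. Categorising lowers sensitivity further: about 11 to 17% detection of 5 ms, against about 51 to 94% for a baseline-adjusted mean.

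A reader might infer three stronger things that the documents and figures do not support:

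- **That pooling hides most of a real QTc effect.** At least two thirds survives in the comparison with placebo when both peak ECGs and the EoBT ECG are present, and an effect near 20 ms would show in the planned tables.
- **That the EoBT ECG is off-drug.** It can fall anywhere from 0 to 14 days after the last dose, and selinexor patients who continue open-label "must complete the EoBT Visit before their next scheduled selinexor dose to maintain continuity of selinexor dosing". It is untimed, not necessarily off-drug.
- **That only the highest value is analysed.** A threshold/range summary is also planned, although its cut-offs and the values it uses are not stated.

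**What to change.** In SAP 5.5:

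1. Add, by arm, the mean change from pre-dose baseline in QTc (one stated correction formula), PR, QRS and heart rate at Cycle 1 Day 1 and Cycle 2 Day 1, with the baseline-adjusted selinexor-minus-placebo difference and 95% CI, labelled descriptive.
2. Show the EoBT ECG separately.
3. State which ECGs count as on-study in each arm, covering unscheduled ECGs, open-label ECGs of selinexor rollover patients, and EoBT ECGs taken on the first open-label dosing day.
4. Keep the shift and threshold tables, which serve to find outliers.

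The cost is one extra table from data already collected, with no new visits and no use of alpha.
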